2.3 Participant flow and endpoint ascertainment

Recall that the primary analysis excludes participants who outmigrated or transferred care. The remaining participants are then classified as virally suppressed (HIV RNA<400 cps/mL) or otherwise (a.k.a., “failures”). To further understand the measurement and endpoints of participants, we will report the number and proportion of participants in the following mutually exclusive and exhaustive categories:

- Outmigrated
- Transferred care within the study region
- Measured viral load (among those not transferred and remaining in the study region)
- Died (among those not transferred and remaining in the study region)
- Otherwise have a missing endpoint viral load

These metrics will be reported overall and by arm.

Additionally, for both the primary analytic population (excluding outmigrations and transfers) and secondary analytic population (including outmigrations and transfers), we will provide the arm-specific number and proportion of participants who are suppressed, unsuppressed, dead, or missing at two-years. These raw proportions differ from the primary analysis, which contrasts the average of the clinic-level proportions by arm and adjusts to increase precision.

2.4 Predictor analyses

In addition to the previously described subgroup analyses, we will conduct the following analyses to elucidate outcome predictors. As outcomes, we will consider being classified as a “failure” (i.e., viral non-suppression, dead, or otherwise missing); having viral non-suppression or dying (adjusting

for missingness), and having viral suppression (adjusting for missingness and censoring at death). Sensitivity analyses will exclude participants with missing endpoint viral loads.

Within each arm separately, we will estimate unadjusted associations and adjusted associations with these outcomes. Baseline predictors will include occupation, marital status, being a parent, drinking alcohol, and mobility. Adjusted analysis will additionally control for country, sex, age, and baseline care group. Adjusted analyses will treat each baseline predictor, in turn, as the exposure variable and the remainder as the adjustment set. All analyses will be implemented with the Single-Stage TMLE and yield associations on the relative scale (statistical analogs of the causal risk ratio).

3 Impact of the roll-out of dolutegravir

During the study follow-up, dolutegravir (DTG) was rolled out across both Kenya and Uganda. According to Ministry of Health guidelines, participants with a recent (within 6 month) viral load <1000 cps/mL were eligible to switch to DTG; however, concerns of neural tube defects may have led to delays in switching for women of reproductive age, who represent the majority of our study population. Additionally, DTG is known to be more robust at achieving viral suppression than prior ART regimens. Therefore, we plan to conduct the following analyses to understand the impact of the DTG rollout on study results.

Overall, by study arm and by sex, we will report the number and proportion of participants who were on DTG at baseline as well as the number and proportion who switched to DTG during study follow-up. Then using the Kaplan-Meier method, we will estimate the longitudinal probabilities of switching to DTG, with censoring at death, endpoint viral load ascertainment, and database closure. Using the two-stage approach and the same approach to covariate adjustment, we will estimate the intervention effect on the cumulative probability of switching by 6, 12, 18, and 24 months. We formally test the corresponding null hypotheses that the probability of switching was equal between arms (relative risk=1) using a two-sided test at the 5% significance level. Additionally, we will create Kaplan-Meier plots for time-to-switch, by arm, by sex, and by clinic.

Second, we will stratify on switch status and evaluate the intervention effect on viral suppression at 2 years. Among participants who switched to DTG during follow-up, we will test the null hypothesis that the intervention did not improve the probability of viral suppression using a one-sided test at the 5% significance level. Likewise, among participants who did not switch to DTG during follow-up, we will test the null hypothesis that the intervention did not improve the probability of viral suppression using a one-sided test at the 5% significance level.

Since switching is a post-baseline variable and potentially impacted by the intervention, we are losing (i.e., blocking) some of the intervention effect by stratifying on it. In other words, formal mediation analyses are warranted. These analyses would allow us to examine the controlled and natural direct effect of the SEARCH-Youth intervention on viral suppression, accounting for switching to DTG as a mediator [15, 16]. However, substantial methodological work remains to modify these methods for cluster randomized trials. Additionally, we expect that in the future, most, if not all, participants

will be on DTG. Therefore, we will instead formally examine the intervention effect on the joint probability of switching to DTG and attaining viral suppression at 2 years. We will again test the corresponding null hypothesis with a one-sided test at the 5% significance level.

All analyses will be conducted for the primary analytic population (excluding outmigrations and transfers) and secondary analytic population (including outmigrations and transfers). All analyses will be subset on participants who are not on DTG at baseline.

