8.1.2 SEARCH YOUTH INTERVENTION AND CLINICAL OUTCOMES

Clinic Sites Randomized to SEARCH Youth Intervention

- Participants will be screened to determine if they meet eligibility criteria. These participants may be already engaged in care, newly re-engaged or recently diagnosed participants, including those who have linked from youth testing activities. A waiver of consent will be obtained to confirm eligibility during the screening process.

- If participants meet eligibility criteria, they will be approached to discuss the study and, if interested, provide informed consent.
- Contact information will be collected, including home location and mobile phone number(s) if available.
- Baseline information will be collected including but not limited to education, occupation, and ART status.
- The SEARCH Youth Intervention will be provided (see section 6.1.1.):
 - i. A Life-Stage Assessment will be performed at the initial visit and at subsequent care visits, generally every 3 months, or more often as needed
 - ii. Participants will be offered visits during routine clinic hours or after standard hours, determined at the initial visit and updated at least annually
 - iii. Participants will undergo VL testing at the baseline and every 6 months thereafter, via rapid point-of-care testing technology. Results will be provided to participants as soon as possible and ideally within 72 hours by mobile phone, via home tracking visits or by scheduled return clinic visit; undetectable results may be provided at the next clinic visit for participants who cannot be reached by mobile phone
 - iv. As needed, providers and local investigators will participate in WhatsApp secure messaging to discuss approaches and solicit feedback for challenging participant-related situations, including but not limited to detectable VL results or barriers to adhering to clinic visits

Clinic Sites Randomized to Control

- Participants will be screened to determine if they meet eligibility criteria. These participants may be already engaged in care, newly re-engaged or recently diagnosed participants, including those who have linked from youth testing activities. A waiver of consent will be obtained to confirm eligibility during the screening process.
- If participants meet eligibility criteria, they will be approached to discuss the study and, if interested, provide informed consent.

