9.4.3 ANALYSIS OF THE SECONDARY ENDPOINT(S)

9.4.3.1 SECONDARY CLINICAL OUTCOMES

Secondary Outcomes include retention: Not more than 90 days late to scheduled visit; sustained virologic suppression (< 400 and < 200 c/mL), virologic failure, death, transfer to other medical facility and change to second line therapy.

Secondary Predictors include country, baseline care status, gender, age, pregnancy, education, occupation, marital status, alcohol use, mobility, and other variables captured in the Life-stage (assessment tool; intervention arm only).

Analytic Plan: The secondary clinical outcomes will be examined using analogous Two-Stage approach, described in section 9.4.2. In secondary analyses, we will also evaluate predictors of sub-optimal outcomes using TMLE (primary) and with univariate associations (secondary), overall and stratified by intervention arm. Based on our prior studies with HIV clinics and follow-up in the two regions we anticipate a 2-year LTFU rate of less than 8%. Regardless of the LTFU level, we will implement enhanced participant tracking procedures that have proven successful in our group at re-engaging participants in care.

Secondary Analyses for Exploring Intervention Component Mediation and Moderation: To explore mechanisms by which the multiple intervention components effect changes in study outcomes, secondary analyses will investigate whether measures of intervention component activities delivered to study participants listed in Table 4 mediate relationship between intervention group assignment (study arm) and viral suppression, and whether sex, age, and region moderate those associations. In line with recent NIH guidelines recommending consideration of sex as a biological variable, participant gender will be a key moderator in these analyses. Mediation and moderation will be assessed using the causal inference-based approach of Valeri and VanderWeele, which yields optimal estimates of indirect effects in the presence of non-continuous (e.g. binary) outcomes and moderator-mediator interactions.²⁰ Mplus will be used to fit causal mediation models because it can adjust standard errors for clustering of participants within communities and clinics/providers, a feature of the proposed study, and because it can include multiple mediators simultaneously.^{21,22} For each mediator, we will include the proportion of the total effect explained by the mediator.

Table 4. Intervention Component Mediators and Measures

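### SAP 2.4 estimates predictor associations only within each arm and omits education and pregnancy, whereas Protocol 9.4.3.1 plans them overall and by arm and names both variables

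*SAP*

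**What the plan says.** **Protocol 9.4.3.1** evaluates predictors of sub-optimal outcomes "using TMLE (primary) and with univariate associations (secondary), overall and stratified by intervention arm". Its list reads "Secondary Predictors include country, baseline care status, gender, age, pregnancy, education, occupation, marital status, alcohol use, mobility", followed by variables from the life-stage tool (intervention arm only).

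**SAP 2.4** states: "Within each arm separately, we will estimate unadjusted associations and adjusted associations with these outcomes". No analysis over both arms is named. The list is: "Baseline predictors will include occupation, marital status, being a parent, drinking alcohol, and mobility". Then: "Adjusted analysis will additionally control for country, sex, age, and baseline care group". Each predictor takes its turn as exposure and the others join the adjustment set. On the estimator: "All analyses will be implemented with the Single-Stage TMLE and yield associations on the relative scale".

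**Education is collected.** Protocol 8.1.2 says: "Baseline information will be collected including but not limited to education, occupation, and ART status". That sentence stands among the procedures for intervention clinics, but the schedule of activities (Protocol 1.3) puts the baseline questions in both arms, and SAP 1.2 tabulates education by arm.

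**No reason is recorded.** SAP 7.1 names the protocol analyses that it leaves to other plans: cost-effectiveness, alcohol use and infant HIV-free survival. The overall predictor analysis, education and pregnancy are not mentioned.

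**The concern.** The predictor analyses are meant to show which young people end the trial dead, unsuppressed or without a viral load. Three things follow from the SAP text as it stands.

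- An association that is the same in both arms never receives its most precise estimate. Each reported interval rests on 14 of the 28 clinics.
- The two arms yield parallel lists of estimates and no contrast between them. A reader who wants to know whether a predictor acts differently under the intervention has only two intervals of unequal precision to set side by side.
- Because each predictor is adjusted for the rest of the list, a variable missing from the list is missing from every adjusted estimate. Schooling plausibly relates to occupation, marriage and parenthood, and also to adherence.

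**Working it through.** **1. Comparison of the texts**

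| | Protocol 9.4.3.1 | SAP 2.4 |
|---|---|---|
| Strata | overall and by arm | by arm only |
| Education | predictor | neither predictor nor adjuster |
| Pregnancy | predictor | neither predictor nor adjuster |
| Parenthood | not named | predictor |

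**2. Design inputs.** The documents give no precision figure for the predictor analyses, so the only stated figure to reproduce is the SAP 7.2 power statement. Inputs: 14 clinics per arm, m = 50, k = 0.175, 65% rising by 24% in relative terms (0.65 × 1.24 = 80.6%), two-sided 5%, 80% power.

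c = 1 + (1.960 + 0.842)² × [(0.65×0.35 + 0.806×0.194)/50 + 0.175²(0.65² + 0.806²)] / 0.156² = 14.07 clinics per arm.

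Power at 14 clinics is 79.8%, so the figure reproduces and the planning rates can be used below. Protocol 9.2 gives a second pair, 64% and 88%.

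**3. Equal information per arm.** With the same association in both arms and variance V in each, the combined variance is V/2. SAP section 2 sets 26 degrees of freedom for all analyses, so the t quantile cancels and the width ratio is √2 = 1.41.

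**4. Planning rates.** For a binary predictor with prevalence q and a risk ratio near 1, in n participants with outcome risk p:

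Var(log RR) = [(1−p)/p] × [1/(nq) + 1/(n(1−q))]

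With equal n and q in both arms, the information in an arm is proportional to p/(1−p). For failure at 35% and 19.4%:

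- control: 0.35/0.65 = 0.538
- intervention: 0.194/0.806 = 0.241
- sum: 0.779
- width ratio, control: √(0.779/0.538) = 1.20
- width ratio, intervention: √(0.779/0.241) = 1.80

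The table gives the by-arm width divided by the overall width. The overall analysis is taken either as arm-adjusted (information added over arms) or as a crude pool at the average risk.

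| Outcome, control vs intervention | Arm-adjusted: control / intervention | Crude pool: control / intervention |
|---|---|---|
| Failure 35% vs 19.4% | 1.20 / 1.80 | 1.18 / 1.76 |
| Failure 36% vs 12% | 1.11 / 2.26 | 1.06 / 2.15 |
| Suppression 65% vs 80.6% | 1.80 / 1.20 | 1.70 / 1.14 |
| Suppression 64% vs 88% | 2.26 / 1.11 | 1.89 / 0.93 |

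One cell falls outside the general range. With suppression at 64% and 88%, the crude pool is less precise than the intervention arm alone (0.93), because it is evaluated at the average risk of 76%. The arm-adjusted analysis does not have this feature.

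These ratios assume equal design effects in the arms and overall. Predictor risk ratios of 1.2 for failure and 0.9 for suppression, at prevalences of 20% and 50%, were also tried. The largest move among the arm-adjusted ratios was from 2.26 to 2.03.

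**5. Education.** The documents give no association of education with any predictor or outcome, so neither the size nor the direction of the resulting bias can be calculated.

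**The case against.** The strongest reply is that by-arm estimation is a sound choice. The intervention acts on work, relationships, residence and alcohol through the life-stage actions in Protocol 6.1.1 (Table 3), so the associations may differ by arm and a pooled figure would average them. The protocol also plans by-arm estimates, whose width would not change if the overall analysis came back. This stands. It is a reason to keep the by-arm estimates and not to rank the pooled one above them. It does not explain why the overall analysis disappeared.

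The SAP list may be open-ended, and pregnancy may have been left out because SAP 2.4 deals with baseline variables; SAP 3.1 allows a look at postpartum status. That is plausible for pregnancy, but it is not written down. Education is a baseline variable, so the explanation does not cover it.

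A reader might infer more than the documents support in two places.

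- *Intervals 40-50% too wide.* The 41% needs equal information per arm and one common association. The 50% also needs 12 degrees of freedom within an arm (√2 × 2.179/2.056 = 1.50), whereas the SAP states 26 for all analyses. By-arm and overall associations are also different quantities unless the association is common to both arms.
- *Clinic-level confounding.* The adjustment set contains country but nothing at clinic level, so such confounding is possible. The documents do not show that it exists. It does not come from by-arm estimation, and an overall analysis with the same covariates would carry it too.

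**Conclusion.** The mismatch is real and unexplained: SAP 2.4 drops the overall predictor analysis, education and pregnancy, all of which Protocol 9.4.3.1 names.

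The cost in precision is a factor of 1.41 under equal information. At the planning rates it is uneven: about 6-20% in the more informative arm and 70-126% in the other, apart from the crude-pool exception noted above. For failure, the intervention arm is the less informative one; for suppression, it is the control arm. All of this rests on an association common to both arms, similar predictor prevalence and numbers per arm, and equal design effects.

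Omitting education leaves the adjusted associations for occupation, marital status and parenthood open to confounding of unknown size.

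The consequence is modest. These are secondary association analyses, and neither the primary estimate nor its test is touched. The documents support neither a blanket 40-50% loss nor a finding that clinic-level confounding is present.

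**What to change.** In SAP 2.4:

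- Restore the overall analysis, with both arms pooled and arm in the adjustment set, alongside the by-arm estimates.
- Add a predictor-by-arm contrast for each predictor. It will be imprecise: with equal information its standard error is √(V + V) = 1.41 times that of a by-arm estimate. It should be reported with its interval and not read as proof of similarity.
- Add education to the predictor list, which also places it in the adjustment set for the others.
- Add pregnancy, or record in SAP 7.1 why it is dropped.

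If clinic-level confounding is to be examined, make it a separate sensitivity analysis, either with clinic indicators replacing arm and country or with clinic-level baseline covariates. Clinic and arm indicators cannot be used together, because each clinic belongs to one arm and one country and the terms are collinear. Clinic indicators may also leave sparse cells.

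The cost is SAP wording and further model runs. Education is already collected, so it needs no new data.

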3.1 Other potential mediators

Other potential effect mediators include

- switches to second-line therapy
- engagement in care, defined as having any clinic contact in the 6 months preceding the endpoint window
- postpartum status, defined as in two ways: (i) reporting a birth within 6 months of the endpoint viral load measurement, and (ii) reporting a birth within 12 months of the endpoint viral load measurement

To understand the impact of these post-baseline events on viral suppression and other secondary endpoints (described below), we may conduct analogous analyses as for the switch to DTG.

4 Secondary health endpoints

We will evaluate the SEARCH-Youth intervention effect on the following secondary endpoints. For each secondary endpoint (unless noted), a Single-Stage TMLE will be used to evaluate the intervention effect. We will use the same approach to define the primary and secondary analytic populations as for the primary endpoint (viral suppression at 2 years). We will also use the same approach to covariate adjustment, consider the same subgroups, and may implement analogous predictor analyses.

4.1 Mortality

We will report the number and proportion of participants who died during study follow-up, overall and by study arm. We will also describe the cause of death. Using the single-stage approach described above, we will test the null hypothesis that the SEARCH-Youth intervention did not reduce the two-year incidence of mortality with a one-sided test at the 5% significance level. Additionally, we may visualize the survival curves with arm-specific Kaplan-Meier plots, pooling over clinics and censoring at outmigration, transfer, and database close.

4.2 Documented transfers

We will report the number and proportion of participants who formally transferred clinical care during study follow-up, overall and by study arm. Evidence of transfers will be documented from clinical records. Using the single-stage approach described above, we will test the null hypothesis that the SEARCH-Youth intervention did not increase the two-year incidence of transfers with a one-sided test at the 5% significance level. Additionally, we may plot the estimated time-to-transfer in each arm, using the Kaplan-Meier method, pooling over clinics and censoring at death and database close.

4.3 Care engagement

We will conduct the following analyses, aiming to capture the multiple ways in which care engagement impacts participants outcomes. Overall and by study arm, we will report the number and proportion of participants who are

- **Engaged at two years:** having any contact with the clinic in the 6 months preceding the start of their endpoint window
- **Retained throughout follow-up:** having contact with the clinic at least once every 120 days since enrollment

where “clinic” refers to the original clinic where the participant enrolled in the study.

For each of these endpoints, we will use the single-stage approach, described above, to obtain point estimates and statistical inference. We test the corresponding null hypotheses with a one-sided test at the 5% significance level. In sensitivity analyses for engagement at two years, we will consider transfers as a success and censor at death. We will also provide clinic-specific estimates of care engagement and retention.

Pending data availability, we may also use the Kaplan-Meier method to estimate the longitudinal probabilities of **lapse**, defined as the first instance of a gap in contact for >120 days, with censoring at death, outmigration, transfer, and the start of the endpoint window. Using the two-stage approach, we will estimate the intervention effect on the probability of lapse by 6, 12, 18, and 24 months and formally test the null hypothesis.

4.4 Severe adverse events

Because the SEARCH-Youth trial does not include any drugs or clinical treatments, adverse events directly related to study intervention are not anticipated. However, we will track and report unexpected and significant adverse events.

5 Patient satisfaction surveys

To assess mechanisms through which the intervention operates, we will administer a patient satisfaction survey during endpoint data collection. The survey aims to assess what works and what does not work for clients at their clinic. The survey covers potential barriers to and facilitators of care engagement and delivery. Specific dimensions include appointment convenience, ease of provider contact, alternative mechanism for clinic contact (i.e., phone visits), alternative mechanisms for drug delivery, trust in the provider, the provider's ability to care for young people with HIV, and overall satisfaction with the clinic. Exact survey questions are available elsewhere.

The survey questions will elicit Likert-type, evenly spaced responses, ranging from strongly disagree to strongly agree. In line with standard practice for such outcomes [11], we will evaluate them quantitatively. We will provide summaries of responses overall, by arm, and by clinic. We will formally test the null hypothesis that the SEARCH-Youth intervention did not reduce barriers to care delivery for adolescents and youth with HIV with a one-sided test at the 5% significance level. To do so, we will use the two-stage approach, first calculating the clinic-specific, average response and comparing these averages between randomized arms. Comparisons of these endpoints will be made on the absolute (i.e., difference) scale.

6 Intervention implementation

Within the intervention arm only, we will also describe intervention implementation. Key metrics will include

- Number and proportion of participants who received 4+ life-stage assessments over the two-year follow-up period
- Summaries of alternative choice access (e.g., off-site appointment, phone appointment, off-hours appointments, and off-site drug delivery), overall and by clinic
- Median time to delivery of rapid viral load results, overall and by clinic
- Proportion of viral load results delivered within 72 hours, overall and by clinic
- Summaries of the counts and content of the provider e-collaborative chats

All metrics will restrict to the primary study population: participants enrolled prior to December 1, 2019 and who remain in the region during the study period.

7 Appendix

[figure not shown]
